1

Research protocol

4th National Registry of Cardiovascular Surgery (CCV) in Argentina

-Version N ° 3- 8 of JULY 2021

Page 2

2

Confidentiality notice: The concepts and information included in this document are confidential and exclusive and not they must be disclosed in whole or in part without the express written consent of the coordinator.

Page 3

3

PROTOCOL SUMMARY

> Title

1- Prospective registry of patients undergoing CCV in Argentina

> Study Phase

1- Prospective Registry (IV)

> Evaluation

1- Follow-up of patients during hospitalization and 30 days after surgery.

> Primary Objectives

^{1.a.}

Determine the evolution and surgical complications in patients undergoing CCV

^{1.b.}

To determine the association between different risk variables during the intranosocomial stay and at 30 days of discharge including nosocomial readmission during the 30-day follow-up.

> Secondary Objectives

To determine the association between different variables that occurred before, during and after the surgical intervention.

To determine the association between different variables of risk at discharge and the rate of complications, including

mortality and readmissions during the 30 days following discharge, such as:

Cardiovascular mortality, all-cause mortality, rehospitalization, infectious complications.

To determine the association between different variables with cardiovascular mortality in relation to CCV.

Assess eventual complications 30 days after hospital discharge

Page 4

4

> Study Design

National, multicenter, analytical, prospective cohort study for prognostic evaluation in patients undergoing cardiovascular surgery (CCV)

> Sample Size

The largest number of patients (between 2000 and 3000) will be enrolled during a set period of time (1 year), from

October 1, 2020 to September 30, 2021

> Eligibility Criteria

Over 18 years

Myocardial revascularization surgery

Valvular surgeries

Ascending Aortic Surgery

Type A Aortic Dissection Surgery

Combined surgery

➤ **Exclusion Criteria**

Cardiovascular surgery for congenital pathologies

Peripheral vascular surgery

Cardiovascular surgery secondary to trauma

Thoracic and abdominal aorta pathology

Other surgeries

➤ **Procedures**

Various centers are included nationwide with a CCV service capable of admitting and intervening patients with criteria already established.

They are arranged below:

Leben Health

Private Hospital Santa Clara de Asis

[name] Hospital

Pasteur Clinic

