The principal investigators of the study are:

[name]

[name]

It will be assigned during the inclusion of investigator patients for each of the centers, who will be responsible for completing the form (*CRF*) and sending the registered data.

7

Additional Information

Introduction

More than ten years have passed since the last CCV registration in the Argentine Republic

In recent decades, the evolution of CCV has shown a reduction in the rate of complications and mortality in centers

specialized

objectives

Record

1. determine complications, mortality and hospital stay, as well as evolution at 30 days after CVD

In our country

2. Compare our variables with those exposed by the different international scores and thus be able to predict the

estimated evolution of our patients.

Substudy

1. Determine the association between different variables, complication rate and mortality 30 days after discharge.

Proposed design

The study consists of **2 stages** , with the voluntary participation of the different centers, which is divided into nosocomial phase and phase a

30 days after discharge

Prospective multicenter registry of prognostic correlation with various risk scores in patients undergoing CCV and

evolution of the same 30 days after discharge

Material and methods

Patients who meet the eligibility criteria described above are included from October 1, 2020

The protocol consists of 2 stages:

1) Nosocomial Phase: a descriptive record is made of the referred variables and the risk parameters upon discharge from

the patients

2) 30 days after discharge, the respective forms will be filled out for the final evaluation of patients who have undergone CCV and discharged from participating institutions

8

Specific Protocol (Operational Definition of Variables):

A complete clinical history of the patient is taken (according to usual practice) and the data is filled out in the Pre, Intra and Post-surgical stage according to what is established in the form

Affiliate Information and Background

Record ID _____

Date of admission _____

Acronyms for Name and Surname _____

Last 3 digits of document number _____

(Last 3 digits only)

Age _____ gender _____ Weight (kg) _____ Height (cm) _____

Public Hospital Coverage

PAMI

Social work

Prepaid

Particular

Telephone

Phone 2 _____

Email _____

Background

Arterial hypertension Yes No

Diabetes Yes No

Diabetic retinopathy Yes No

Dyslipidemia Yes No

Ex-smoker tobacco

I never smoke

Smokes daily

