Smokes occasionally

It is unknown

9

Hyperuricemia Yes No

HIV Yes No

Systolic LV dysfunction Yes No

Heart failure Yes No

Myocardial infarction No <30 days> 30 days

Myocardial revascularization surgery Yes No

Valve surgery Yes No

Other cardiovascular surgery Yes No

Type of cardiovascular surgery

(Describe ...)

Coronary angioplasty Yes No

Immunocompromise Yes No

Mediastinal radiation Yes No

Stable chronic angina Yes No

Chronic atrial fibrillation Yes

No

Unstable angina Yes No

Family history of coronary disease Yes No

Peripheral vascular disease Yes No

Pulmonary Hypertension Yes No

Cerebrovascular disease Yes No

Syncope Yes No

SAHOS Yes No

COPD No

Mild

Moderate

Severe

It is unknown

Remote Non-Recent Pneumonia
It is unknown
Did you have COVID-19 within the month prior to surgery? If not
Liver disease Yes No
Illicit drug use No Recent Remote
It is unknown
Alcohol abuse No
<1 glass per day
2 to 7 glasses per day
> 7 glasses per day
It is unknown
Usual medication Aspirin

10
Clopidogrel
Ticagrelor
Prasugrel
Statins
Beta-blockers
ACEI
ARA-II
Loop diuretics
Thiazides
Spirinolactone
Insulin
Oral hypoglycemic
Anticoagulants
Suspension P2Y12 Inhibitors Yes No
Days of suspension of Inhibitors P2Y12

Frail patient Yes No
I use a fragility score Yes No
Fragility score

Other background

Presurgical data

Presurgical diagnosis Heart failure
Endocarditis
Acute aortic syndrome
Ischemic heart disease
Valvular disease
Pericardial involvement
Other
Related signs and symptoms Dyspnoea
Precordial pain
Edema in lower limbs
Febrile syndrome
Syncope
Palpitations
Neurological focus
Acute Pulmonary Edema
Tachyarrhythmias
Bradyarrhythmias
Other

eleven
(Select at least one)
Coronary heart disease Yes
No
Left Coronary Trunk Injury Yes

No

Number of glasses _____

Vessels affected Descending Anterior _____

Diagonal _____

Circumflex _____

Lateroventricular _____

Right Coronary _____

Other _____

Valvular disease Yes _____

No _____

Type of valve pathology Aortic stenosis _____

Aortic insufficiency _____

Mitral stenosis _____

Mitral Insufficiency _____

Pulmonary stenosis _____

Pulmonary insufficiency _____

Tricuspid stenosis _____

Tricuspid Insufficiency _____

(Select at least one)

Combined Surgery Yes _____

No _____

(Valular + Bridges)

Type of procedure Scheduled _____

Urgency _____

Emergency _____

Laboratory upon admission

Hematocrit _____ Leukocytes _____ Platelets _____

Blood glucose _____ Uremia _____ Creatinine _____

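### The alcohol item has no category for an intake of 1 to under 2 glasses per day, and no rule says how to code it

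*Protocol*

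**What the plan says.** The case report form is printed in the protocol under the heading "Specific Protocol (Operational Definition of Variables", which makes it the definition of the recorded variables. In its Background block, the alcohol item opens with "Alcohol abuse No". Three intake levels follow: "<1 glass per day", "2 to 7 glasses per day" and "> 7 glasses per day". The last option is for unknown intake. The protocol contains no note, footnote or rounding rule for this item.

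Among the Secondary Objectives in the Protocol Summary is "To determine the association between different variables that occurred before, during and after the surgical intervention". Alcohol intake is one of the preoperative variables available for that purpose. The Protocol Summary plans 2,000 to 3,000 patients, enrolled from 1 October 2020 to 30 September 2021. The title page dates Version 3 to 8 July 2021.

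**The concern.** A categorical item should give every possible answer exactly one code. Here the lowest intake category stops below 1 and the next starts at 2. One glass a day is a natural answer to the question and cannot be coded correctly. Whoever completes the form must pick a code that does not describe the patient.

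At stake is the quality of one covariate. Patients at this level may be spread over neighbouring categories, which blurs the step between low and substantial intake in any association analysis that uses the item. An analysis plan can decide how to group recorded categories, but it cannot recover a level that was never recorded.

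**Working it through.** No sample size, power or error-rate figure is involved. The check is whether the listed options cover every intake x, in glasses per day.

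**Coverage of the options (Protocol, Background block)**

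| Option | Intake covered |
|---|---|
| No | x = 0 (see below) |
| Lowest category | 0 < x < 1 |
| Middle category | 2 ≤ x ≤ 7 |
| Highest category | x > 7 |
| Unknown | intake not known |

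The known-intake options together cover x < 1 and x ≥ 2. The uncovered range is 1 ≤ x < 2, which includes x = 1. There is no gap at the upper boundary: 7 belongs to the middle category and anything above it to the highest.

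**Where such a patient could go**

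- *No.* The item is headed as abuse, so a clinician could tick No to mean no abuse. But a separate option for under one glass implies that No means no intake. A one-glass drinker coded No would rank below someone who drinks less.
- *Under 1.* This understates intake.
- *2 to 7.* This overstates intake. Against the lower bound of the category, the ratio is 2/x: 2/1 = 2.00 at one glass, 2/1.5 = 1.33 at 1.5 glasses, and 2/1.9 = 1.05 at 1.9 glasses.
- *Unknown.* This is untrue, because the intake is known.

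**Comparison within the form.** The postoperative extubation item runs from under 6 hours to 6–12, 12–24 and over 24. There, the category after the under-6 one starts at 6. By that pattern, the category after under 1 would start at 1.

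**Could a lost sign explain it?** If the lowest category had been at most 1, exactly one glass would be covered, but 1 < x < 2 would still have no code.

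**Scale.** The protocol does not give the share of patients in the gap. Each percentage point of the cohort would be 0.01 × 2,000 = 20 to 0.01 × 3,000 = 30 records. The documents do not say how many points apply.

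**Timing.** From 8 July to 30 September 2021, both days included, is 24 + 31 + 30 = 85 days. The enrolment year has 365 days, and 85/365 = 23%. About 77% of the enrolment period had passed by the Version 3 date.

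**The case against.** The strongest reply is that this is one of dozens of baseline items, that no objective names alcohol, and that how the variable is grouped or modelled belongs to the analysis plan. The printed text is also visibly a rough translation. The coronary section asks for a number of glasses where vessels are evidently meant, and a comparison sign in the perioperative infarction criteria came out garbled. A point that turns on one sign and one digit may reflect the translation and not the form that sites use.

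Much of this stands. It limits the severity and makes a check against the original-language form the first step. It does not remove the gap: the alcohol labels are legible as printed, the garbled sign elsewhere did not come out as a clean less-than sign, and grouping in an analysis plan comes after the information has been lost.

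A reader might also infer more than the documents support:

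- *That coding to the 2–7 category at least doubles the intake.* Against that category's lower bound, this holds only at exactly one glass.
- *That a definite number of patients is miscoded.* Any such count needs a prevalence that the protocol does not give.
- *That the gap creates spurious differences between centres.* Centres could code differently, since each has its own investigator completing the form, but nothing shows that they do.

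**Conclusion.** The point holds at low severity. As printed, the item is not exhaustive. Intake from 1 to under 2 glasses per day has no valid code, four wrong destinations are open, and the record does not reveal which was used. The effect is misclassification of one preoperative covariate. No outcome or eligibility criterion is touched, and the size cannot be computed from the documents. The conclusion assumes that the printed labels match the form in use and that No means no intake. If No is read as no abuse, its meaning is itself unclear and needs defining.

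**What to change.** 1. Check the labels, including the per-day period, against the form in its original language.
2. If the gap is confirmed, add an option for 1 to under 2 glasses per day. Existing codes then keep their printed meaning. Starting the middle category at 1 would also close the gap, but that code would then mean different things before and after the change.
3. Send sites a short coding note covering this level and the meaning of No.
4. Flag records entered before the change. Report alcohol results from them with the coding limitation stated. Do not merge the under-1 and 2–7 categories: that would pool very light drinkers with people drinking seven glasses, erase the gradient of interest, and still miss patients entered as No or unknown.

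The cost is one option on the form, a note and a flag. The downside is that earlier records keep the old coding. If the change took effect on the Version 3 date, it would cover at most the last 85 days of enrolment, so for most of the cohort the stated limitation is the main remedy.

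### The presurgical signs-and-symptoms item requires at least one selection but has no code for a patient with none, so that reference group is lost

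*Protocol*

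**What the plan says.** In the Presurgical data part of the form, the item beginning "Related signs and symptoms Dyspnoea" offers ten named findings, the last of them "Bradyarrhythmias", and then *Other*. Only a page number stands between *Other* and the note "Select at least one".

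The same note follows the valve list that begins "Type of valve pathology Aortic stenosis", but a Yes/No question on valvular disease comes before that list. Other multi-level items carry their own negative level, for example "Illicit drug use No Recent Remote".

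The Eligibility Criteria are defined by age and type of operation. Elective cases are expected, since urgency is recorded as "Type of procedure Scheduled", urgent or emergency. The Specific Protocol section says that data are filled in as the form establishes. One secondary objective is "To determine the association between different variables that occurred before, during and after the surgical intervention". Planned enrolment is "between 2000 and 3000" patients.

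**The concern.** A form that demands an answer should allow a true answer for every eligible patient. Here a patient with neither a related sign nor a symptom, for example one whose scheduled valve or ascending aortic operation was decided on imaging, has no code.

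The preoperative presentation is one of the variables that the objectives relate to complications and death. The patients without findings are its natural reference group. If they are spread over *Other*, listed symptoms and blanks, patients with and without findings cannot be compared, and *Other* no longer means an unlisted finding. An analysis plan cannot restore a category that was never collected, so this belongs to the protocol and its form.

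**Working it through.** The documents give no figure to reproduce, so the check is mainly a reading of the form.

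**1. Does the note belong to this item?** Yes. It comes directly after the last option. The next item, on coronary disease, is a plain Yes/No, to which such a rule cannot apply. The form also puts its other notes (units, minutes) after the field they govern.

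**2. Is there a negative route?**

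| Item | Yes/No question first | Negative level | At-least-one note |
|---|---|---|---|
| Signs and symptoms | no | no | yes |
| Valve pathology | yes | not needed | yes |
| Illicit drugs, COPD, alcohol | no | yes | no |

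Only the symptom item has the rule and no way to record a negative.

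**3. Can such patients be enrolled?** Yes. No criterion requires symptoms, and scheduled procedures are recorded.

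**4. Can another field recover them?** Not cleanly. Background has Yes/No items for heart failure, stable and unstable angina, and syncope. There is no functional class, no symptomatic/asymptomatic item, and no separate Yes/No for dyspnoea, palpitations or edema. The risk scores are entered only as totals.

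**5. How many patients?** The protocol does not say. Assuming that 5% to 20% have neither sign nor symptom: 0.05 × 2000 = 100 at the low end and 0.20 × 3000 = 600 at the high end.

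**6. What happens to a symptom's association with death?** This depends on where sites put these patients. All inputs here are assumptions: dyspnoea truly present in 50%; mortality 8% with dyspnoea, 5% with other findings, 2% with none; share with none *a*; fraction of those ticked as dyspnoea *f*, the rest staying outside dyspnoea.

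- Mortality recorded with dyspnoea: p1 = (0.50 × 0.08 + f·a × 0.02) / (0.50 + f·a)
- Mortality recorded without: p0 = ((0.50 − a) × 0.05 + (1 − f)·a × 0.02) / (0.50 − f·a)
- Odds ratio = [p1/(1 − p1)] / [p0/(1 − p0)]

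For a = 0.20 and f = 0: p1 = 0.08, p0 = 0.019/0.50 = 0.038, odds ratio 2.20. For a = 0.20 and f = 0.50: p1 = 0.042/0.60 = 0.070, p0 = 0.017/0.40 = 0.0425, odds ratio 1.70.

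| a | f = 0 (all under *Other*) | f = 0.25 | f = 0.50 |
|---|---|---|---|
| 5% | 1.76 (true value) | 1.70 | 1.64 |
| 20% | 2.20 (true value) | 1.93 | 1.70 |

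The effect runs from none to marked on inputs that the documents do not supply. The table shows the mechanism and is not an estimate.

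**7. Timing.** Version 3 is dated 8 July 2021 and enrolment runs from 1 October 2020 to 30 September 2021. By that date 280 of 365 days had passed (77%), with 85 days left.

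**The case against.** The strongest reply is that this is one baseline descriptor on a long form. No comparison of symptomatic with asymptomatic patients is planned, the outcomes are recorded elsewhere, and EuroSCORE II and ArgenScore have their own fields. That stands, and it limits the weight of the point. It does not remove it, because the secondary objective covers preoperative variables in general.

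A reader might infer that every asymptomatic patient is forced into a false entry. The documents do not support that, for three reasons:

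- The item covers signs as well as symptoms. A symptom-free patient with an arrhythmia or lower-limb edema has a truthful answer.
- Nothing says that the rule is enforced electronically, so some sites may leave the item blank.
- *Other* is not a false symptom in the way that a wrongly ticked dyspnoea is. Whether it opens a text field cannot be seen from the document.

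A reader might also take the attenuated odds ratios as the expected bias. They rest on assumed mortality rates and on an assumed share of sites ticking dyspnoea. If sites use *Other*, the dyspnoea odds ratio does not change.

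Finally, *Other*-only records with No on the history items for angina, syncope and heart failure would approximate the missing group. This helps, but those are history items, and they would not find a falsely ticked symptom.

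**Conclusion.** The defect is real and narrow. If the form is completed as written, a patient with neither a related sign nor a symptom has no valid code, and a blank cannot be told from missing data. The reference group for presurgical findings is lost and *Other* is contaminated. This follows from the form alone.

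Inflated prevalence and diluted associations for listed symptoms follow only if some sites tick a finding that is absent, and their size cannot be estimated from the protocol. The count of 100 to 600 patients rests on the assumed 5% to 20%. The share with neither sign nor symptom may be smaller than the share without symptoms. Mortality, complications, readmission and the risk score totals are not affected. The correction is worth making because it is cheap, but the registry's main results do not depend on it.

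**What to change.** Add one exclusive code, *None (no related signs or symptoms)*, and keep the at-least-one rule, so that a blank means missing.

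For records already entered, query those coded only *Other* and those left blank. Where feasible, also query scheduled cases with a single symptom, because a query limited to *Other* would miss falsely ticked symptoms. Note the date of the form change in the analysis, so that the two coding periods can be told apart.

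The cost is one code and a short query round. The downside is two coding conventions within one variable: with at most 85 days of enrolment left after the version date, most records may predate the new code, and the queries matter as much as the code itself. Eligibility, outcomes and patient care do not change.

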Cholesterol _____ HDL _____ LDL _____

Triglycerides _____ Total bile _____ GOT _____

GPT _____

Electrocardiogram

Rhythm _____ Frequency _____

Prolonged PR _____ AV block _____

Right bundle branch block _____ Left bundle branch block _____

ST elevation _____ ST elevation _____

12

T wave inversion _____

SCORES

We ask you to complete the following values by calculating them. Click on the following links to enter the respective online calculators:

EUROSCORE: <https://www.rccc.eu/Cardio/euroscoreII.html>

ARGENSCORE: <http://argenscore.org/calculadora.aspx>

EUROSCORE II mortality (%) _____

ARGENSCORE score _____

ARGENSCORE Mortality _____

Use of pre-surgical IACB Yes No

Use of Swan Ganz presurgical Yes No

Use of presurgical inotropics Yes No

Intraoperative

Date of surgery _____

Patient condition Stable Unstable _____

Use of ventricular assist Yes No

Use of BCIAo Yes No

Required transfusion of blood products Yes No

Red blood cells _____

(Units)

Platelets _____

(Units)

Plasma

(Units)

Extracorporeal circulation Yes No
CEC time

(Minutes)

Clamping time

(Minutes)

CRM was carried out Yes No
Left breast bridge Yes No
Right breast bridge Yes No
Radial bridge Yes No
Number of radial bridges

Page 13

13

Venous bridge Yes No
Number of venous bridges

Endarterectomy Yes No

Quality of the distal beds Good Regular
Bad

Valve surgery was performed Yes No

Aortic valve plastic Yes No

Aortica Jacoub plastic technique

David

Aortic valve replacement Yes No

Type of Biological Aortic Valve with stent

Biological without stent

Single Disc Mechanics

Clamshell Mechanics

Biological valve type Aortic Pericardial

Swine

Bovine

Aortic biological valve measurement

(Number)

Brand of Aortic Biological Valve

Aortic mechanical valve measurement

(Number)

Aortica mechanical valve brand

Ring enlargement Yes No

Ring enlargement technique

Plastic Mitral Valve Yes No

Plastic was made on the previous valve

Posterior leaflet

Mitral valve replacement Yes No

Biological Mitral Valve Type with Stent

Biological without stent

Single Disc Mechanics

Clamshell Mechanics

Type of Mitral Pericardial Biological Valve

Swine

Page 14

14

Bovine

Mitral biological valve measurement

(Number)

Mitral Biological Valve Brand

Mitral mechanical valve measurement

(Number)

Mitral mechanical valve brand

Intra-operative TEE in mitral surgery Yes No

Plastic Tricuspid Valve Yes No

Tricuspid valve replacement Yes No

Biological Tricuspid Valve Type

Mechanics

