
Tricuspid biological valve measurement

(Number)

Brand of Tricuspid Biological Valve

Tricuspid mechanical valve measurement

(Number)

Tricuspid mechanical valve brand

Pulmonary valve plastic Yes No

Pulmonary valve replacement Yes No

Biological Pulmonary Valve Type

Mechanics

Pulmonary biological valve measurement

(Number)

Pulmonary biological valve brand

Pulmonary mechanical valve measurement

(Number)

Pulmonary mechanical valve brand

Ross Surgery Yes No

Page 15

fifteen

Ascending Aortic Surgery Yes No

Type of Ascending Aorta Surgery Bentall de Bono

Resuspension

WHEAT (supracoronary)

Tirone David

Yacoub

Cabrol

Tubular portion replacement

Reattachment of supra-aortic vessels

Other

Aortic prosthesis placement Yes No

Aortic prosthesis measurement

(Number)

Intra-surgical hemorrhage Yes No

Cause of Medical Surgical Bleeding

Intra-surgical arrest Yes No

Readmission to CEC Yes No

Other complications

Postoperative

Via air Fast track (extubate)

Intubated
Extubates at <6 hours
6 to 12 hours
12 to 24 hours
> 24 hours
Long ARM Yes No
ARM days

Reintubation Yes No
Hemorrhage Yes No
(> 500 ml in the 1st hour or> 400 ml in the 2nd hour or
> 300 ml in the 3rd hour or> 200 ml in the 4th hour or
> 100 ml in the 5th hour)
Type of Hemorrhage Medical Surgical
Surgical examination required Yes No
Surgical resolution Yes No
Transfusion of blood products Yes No
Right Ventricular Dysfunction Yes No
(Persistent arterial hypotension, blood pressures

16

Elevated ventricular (right atrium) filling,
low cost with need for intervention
pharmacological and eventually mechanical (TAPSE <17
mm or visual impression by Echocardiography of
RV dysfunction))
Low expenditure syndrome Yes No
(Systolic blood pressure <90 mmHg, pale and
skin coldness, lack of capillary filling,
clouding and oliguria, heart index
<2.2
L / min / m², pulmonary capillary pressure> 18 mmHg, with
inotropic and / or balloon requirement
intra-aortic counterpulsation (IACAB))
Inotropic / vasopressor requirement Yes No
Inotropics / Vasopressors used Dopamine
Dobutamine
Milrinone
Levosinmendan
Noradrenaline
Vasopressin
Adrenalin
Swan Ganz requirement Yes No
Perioperative myocardial infarction Yes No
Definition of perioperative infarction according to the center Development of Q waves
per ... Increased CPK MB \hat{a} % \neq 80 IU / ml
Parietal alterations on echocardiogram
Troponin T or I> 10 times its baseline value
US troponin> 10 times baseline
Atrial fibrillation Yes No

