Atrioventricular block Yes No
Complex ventricular arrhythmia Yes No
Transient pacemaker Yes No
Permanent pacemaker Yes No
I do prophylaxis for postoperative AF Yes No
Drug used

POP day of initiation of prophylaxis for AF

Renal failure Yes No
(Increase in creatinine above 50%
with respect to the baseline value and / or

17

hemodialysis)

Hemodialysis Yes No

Stroke Yes No

(Focal and / or diffuse brain injury confirmed by clinical findings and / or computed tomography with sensory or motor sequelae upon discharge of the patient)

Transient ischemic accident Yes No

Psychiatric disorders Yes No

(Any of the following: delirium, hallucinations, psychomotor arousal)

Required treatment with ... Risperidone

Quetiapine

Haloperidol

Other

Respiratory distress syndrome Yes No

(Infiltrate in 4 quadrants - PCP <18 - PAFI <200)

Fever without obvious focus Yes No

Sepsis Yes No

(Suspected or documented infection with dysfunction of target organ and at least two of the following criteria: Temperature > 38 ° C or <36 ° C, White blood cell count greater than 12,000 uL or less at 4000 uL, Tachycardia, Tachypnea > 30 rpm, Altered mental state, Positive culture of primary focus of infection, mean arterial pressure less than 70 mm Hg for a minimum fingers

hours, poor distal perfusion ("))

Urinary infection Yes No

Respiratory infection Yes No

Surgical wound infection Yes No

Superficial wound infection Yes No

Saphenous wound infection Yes No

Sternal infection Yes No

Mediastinitis Yes No

Sternal reopening requirement Yes No

Sternal reopening POP day

Sternal mechanical instability Yes No

COVID-19 infection development during internment

18

If not

TOTAL days of hospitalization until discharge

POSTOPERATIVE days until discharge

Discharge

Alive

Dead _____

Death cause:

Infectious

Cardiovascular

Distributive shock

Hemorrhage

Cardiac tamponade

Stroke

Respiratory distress

Multi-organ failure

Another cause

Death from infectious cause: Mediastinitis Pneumopathy Sepsis Other

Identified germ

Death from cardiovascular cause: Myocardial infarction Arrhythmia Heart failure

Pre Registration Laboratory

Hematocrit _____ Blood glucose _____

Uremia _____ Creatinine _____

Medication at discharge ASA

Clopidogrel

Ticagrelor

Prasugrel

Statins

Beta-blockers

Sartan

ACE inhibitors

Loop diuretic

Thiazide

Spironolactone

Insulin

Oral hypoglycemic

Anticoagulants

Investigator Notes

19

Follow-up

Re-internment Yes No

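### The postoperative renal items are not limited to new dialysis and no structured field records dialysis before surgery, so chronic dialysis can be reported as a complication; secondarily, the stroke item appears to omit strokes that recover before discharge

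*Protocol*

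**What the plan says.** **Renal.** In the Postoperative section of the form, renal failure is a creatinine rise of more than 50% "with respect to the baseline value and / or" hemodialysis. A separate item, "Hemodialysis Yes No", follows. Neither mentions new onset. The Exclusion Criteria in the Protocol Summary do not mention dialysis. The Background list covers liver disease, COPD, HIV, hyperuricemia and others, but has no kidney disease or dialysis item. Prior dialysis could appear only indirectly: in the free-text Other background and Investigator Notes fields, or through the admission urea and creatinine values. The two risk scores are stored as results only, so their inputs cannot be read back.

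For some conditions the form does record both states. Inotropes have "Use of presurgical inotropics Yes No" and later "Inotropic / vasopressor requirement Yes No". Atrial fibrillation has "Chronic atrial fibrillation Yes" in the history and "Atrial fibrillation Yes No" after surgery.

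**Stroke.** The item requires a brain injury established clinically and/or by "computed tomography with sensory or motor sequelae upon discharge of the patient". The next item is "Transient ischemic accident Yes No", with no definition. Stroke is also a listed cause of in-hospital death, and Dead is one of the discharge statuses. The Follow-up section has no stroke item.

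**The concern.** Primary objective 1.a is to describe the course and surgical complications of these patients. A complication rate needs events that arose after the operation. A patient on chronic dialysis who continues it after surgery satisfies both renal items as written without any new event. Once the data are in, nothing structured separates that patient from one who started dialysis because of the operation. The secondary objective relating pre-, intra- and postoperative variables would use the same field, although it does not name dialysis.

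For stroke the risk runs the other way. If persisting sensory or motor deficit is part of the case definition, a survivor who recovered before discharge is a non-case, and the item does not give the rate of all postoperative strokes. The sentence can also be read so that the sequelae condition applies only to CT-confirmed cases, so centres may code the same patient differently.

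**Working it through.** The protocol gives no dialysis or stroke rate, so there is no stated figure to reproduce. The only document inputs are the 2000–3000 planned patients, the enrolment dates (1 October 2020 to 30 September 2021) and the version date (8 July 2021). Every rate below is an assumption.

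**1. Hemodialysis item.** Let p be the share on dialysis before surgery (0.5–3%), n the new-dialysis rate among the others (2–4%), and k the share of prior-dialysis patients coded Yes.

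Recorded rate = k × p + (1 − p) × n

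| p | n | k | Recorded | Recorded ÷ n |
|---|---|---|---|---|
| 0.5% | 4% | 1 | 0.5% + 0.995 × 4% = 4.48% | 1.12 |
| 0.5% | 4% | 0.5 | 0.25% + 3.98% = 4.23% | 1.06 |
| 0.5% | 4% | 0 | 3.98% | 0.995 |
| 1.5% | 3% | 1 | 1.5% + 0.985 × 3% = 4.455% | 1.49 |
| 3% | 2% | 1 | 3% + 0.97 × 2% = 4.94% | 2.47 |
| 3% | 2% | 0.5 | 1.5% + 1.94% = 3.44% | 1.72 |
| 3% | 2% | 0 | 1.94% | 0.97 |

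Coding practice (k) decides whether there is a problem at all. The number of patients who could be involved is 2000 × 0.5% = 10 to 3000 × 3% = 90.

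**2. Renal failure item.** The same formula applies, with a true incidence of 5–20% in place of n.
- p = 0.5%, true 20%: ratio 1.02 (k = 1) or 1.01 (k = 0.5).
- p = 3%, true 5%: (3% + 4.85%) ÷ 5% = 1.57 (k = 1) or (1.5% + 4.85%) ÷ 5% = 1.27 (k = 0.5).

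**3. What remains after the fix.** Querying every hemodialysis = Yes record corrects the numerator of the hemodialysis rate. In earlier records, prior-dialysis patients coded No may stay in the denominator. If none of them is found, reported ÷ true = (1 − p) ÷ (1 − k × p). The worst case (p = 3%, k = 0) is 0.97, an error of at most 3% of the rate.

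**4. Stroke, natural reading.** Let CF be stroke case fatality (15–35%), s the share of surviving strokes without sensory or motor sequelae (10–30%), and f the share of fatal strokes coded No.

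Capture = 1 − CF × f − (1 − CF) × s

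- f = 0, CF 0.15, s 0.3: 1 − 0.255 = 0.745.
- f = 0, CF 0.25, s 0.2: 1 − 0.15 = 0.85, so a true 2.0% is recorded as 1.70%.
- f = 0, CF 0.35, s 0.1: 1 − 0.065 = 0.935.
- f = 0.25, CF 0.25, s 0.2: 0.85 − 0.0625 = 0.7875.

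Uncounted surviving strokes at 2–3% incidence: 2000 × 2% × 0.65 × 0.1 = 2.6, to 3000 × 3% × 0.85 × 0.3 = 23.0. A wider set of assumptions (1–4% incidence, 10–40% of all strokes recovering) gives 2000 × 1% × 10% = 2 to 3000 × 4% × 40% = 48.

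**5. Reporting survivors only.** In the middle case this would capture 0.75 × 0.80 = 60% of all strokes, against 85% with fatal strokes included. The whole-year figure should therefore keep them.

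**The case against.** On the renal side, the creatinine criterion is relative to baseline, which suggests that a new event is meant. Centres may already code only new dialysis, and then the effect vanishes. The form is also not blind to prior dialysis, since free text and admission creatinine can flag it. Nor does it pair pre- and postoperative fields systematically: the postoperative permanent pacemaker item has no presurgical counterpart either. The inotrope and atrial fibrillation pairs show that such a field fits the form, not that a convention was broken. All this stands and limits the size of the problem. It does not remove it, because the dialysis criterion itself is unqualified and nothing requires prior dialysis to be recorded. An unseen analysis plan cannot supply a field that was never collected.

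On the stroke side, the text is a visibly rough translation, a second reading exists, and a sequelae-based item suits an analysis of risk parameters at discharge. The secondary outcomes named in the summary include neither stroke nor dialysis. These points stand and are why stroke ranks below the renal point.

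A reader might infer that fatal strokes are excluded, or that the association between stroke and mortality is biased in a known direction. The documents support neither. Death is a discharge status, so a deficit present until death can be coded Yes, and the direction depends on coding that the protocol does not fix. Nor is it safe to say that visual deficits are lost, since vision is arguably a sensory function.

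**Conclusion.** The renal point holds and should be fixed. As written, the form lets continued chronic dialysis count as a surgical complication, and no structured field separates it from new dialysis. A reader might infer that the registry's dialysis rate is in fact inflated, perhaps more than twofold. The documents do not show that: the factor of about 2.5 needs the highest assumed prior rate, the lowest assumed new rate and every prior-dialysis patient coded Yes. If centres code only new dialysis, the ratio is 0.97–1.0. The renal failure item is affected less, at most 1.57 under the assumptions used.

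The stroke point is real on the natural reading but secondary. With fatal strokes coded Yes, about 75–94% of strokes would be captured under the stated assumptions, and the absolute number missed is probably small. No claim is made about the direction of bias in the association between stroke and mortality.

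**What to change.** **Renal (main).**
- Add a yes/no item for dialysis before surgery to the Background section.
- For records already entered, query every hemodialysis = Yes record. Screen Other background, Investigator Notes and high admission creatinine (cut-off set in advance) for prior dialysis.
- Report new hemodialysis and renal failure among patients not known to be on prior dialysis. State that a few unidentified prior-dialysis patients coded No may remain in the denominator of earlier records.

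**Stroke (lower priority).**
- For new records, record any postoperative stroke, with sensory or motor sequelae at discharge (Yes / No / died) as a separate field.
- Check in-hospital deaths with stroke as the cause against the stroke item.
- Report the whole-year figure under the current definition with fatal strokes included, labelled as stroke with sequelae at discharge or death. State that it is not the rate of all postoperative strokes.

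**Cost.** The renal change needs one field and a limited number of queries. With k = 1, these are (0.5% + 0.995 × 2%) × 2000 = 50 to (3% + 0.97 × 4%) × 3000 = 206 hemodialysis = Yes records. If accrual is uniform and the change takes effect on 8 July 2021, 280/365 (77%) of these, about 38–158, are retrospective. Screening free text and creatinine adds some work at the coordinating centre.

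The stroke change needs one reworded item and one added field. It applies to only 85/365 of enrolment, about 466–699 patients, and on the assumptions above would recover roughly 2.6 × 85/365 = 0.6 to 23.0 × 85/365 = 5 strokes. Earlier recovered strokes stay missed. The death check does not reach stroke patients who died of another listed cause.
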